8.4. Management of Adverse Events

8.4.1. General considerations

Dose reductions for pembrolizumab and rituximab are not permitted.

The doses of pembrolizumab and rituximab should be delayed as required according to sections below when experiencing a treatment related adverse event. In case of a treatment delay, both drugs should be withheld. This includes AEs related to only one IMP (e.g. a rituximab related AE results in both rituximab and pembrolizumab being withheld).

Treatment cycles should be delayed, and not be omitted as a result of adverse events, and upon resolution treatment should resume at the scheduled cycle.

If any immune-related AE does not resolve within 12 weeks of the last dose of an IMP, or if corticosteroids cannot be reduced to ≤ 10 mg prednisolone or equivalent per day within 12 weeks then treatment should be permanently discontinued. See section 8.5 for full treatment discontinuation details.

Treatment should also be delayed or discontinued if any adverse event, laboratory abnormality, or intercurrent illness which, in the judgment of the Investigator, presents a substantial clinical risk to the subject with pembrolizumab or rituximab dosing.

8.4.2. Pembrolizumab related adverse events

Immune related adverse events

If a patient experiences a pembrolizumab immune-related event, trial treatment should be withheld or discontinued as per the table below.

Where treatment is withheld, treatment should resume once the adverse event has reduced to grade 1 or 0 (as per table below). Corticosteroid taper should be initiated upon the adverse event improving to grade 1 or less and continue to taper over at least 4 weeks. Tapering should be performed as per local clinical practice.

For severe and life-threatening immune related adverse events, IV corticosteroid should be initiated first followed by oral steroid. Other immunosuppressive treatment should be initiated if immune related adverse events cannot be controlled by corticosteroids.

Toxicity Management Guidelines for Immune-related AEs associated with Pembrolizumab

Immune-related AEs	Severity grade CTCAE v5.0	Action taken	irAE management	Monitor and follow-up
Pneumonitis	Grade 2	Withhold treatment	
 Administer corticosteroids (initial dose of 1-2 mg/kg prednisolone or equivalent) followed by taper Add prophylactic antibiotics for opportunistic infections 	
 Monitor participants for signs and symptoms of pneumonitis Evaluate participants with suspected pneumonitis with radiographic imaging and initiate corticosteroid treatment
	Grade 3 or 4, or recurrent Grade 2	Permanently discontinue treatment		
Diarrhoea / Colitis	Grade 2 or 3	Withhold treatment	
 Administer corticosteroids (initial dose of 1-2 mg/kg prednisolone or equivalent) followed by taper 	
 Monitor participants for signs and symptoms of enterocolitis (i.e., diarrhoea, abdominal pain, blood or mucus in stool with or without fever) and of bowel perforation (i.e., peritoneal signs and ileus). Participants with \geq Grade 2 diarrhoea suspecting colitis should consider GI referral and performing endoscopy to rule out colitis. Participants with diarrhoea/colitis should be advised to drink liberal quantities of clear fluids. If sufficient oral fluid intake is not feasible, fluid and electrolytes should be substituted via IV infusion.
	Grade 4 or recurrent Grade 3	Permanently discontinue treatment		
AST / ALT elevation or Increased bilirubin	Grade 2	Withhold treatment	
 Administer corticosteroids (initial dose of 0.5- 1 mg/kg prednisolone or equivalent) followed by taper 	
 Monitor with liver function tests (consider weekly or more frequently until liver enzyme value returned to baseline or is stable)
	Grade 3 or 4	Permanently discontinue treatment	
 Administer corticosteroids (initial dose of 1-2 mg/kg prednisolone or equivalent) followed by taper 	

Immune-related AEs	Severity grade CTCAE v5.0	Action taken	irAE management	Monitor and follow-up
Type 1 diabetes mellitus (T1DM) or Hyperglycaemia	Newly onset T1DM or Grade 3 or 4 hyperglycaemia associated with evidence of β -cell failure	Withhold treatment ¹	
 Initiate insulin replacement therapy for participants with T1DM Administer anti-hyperglycaemic in participants with hyperglycaemia 	
 Monitor participants for hyperglycaemia or other signs and symptoms of diabetes.
Hypophysitis	Grade 2	Withhold treatment	
 Administer corticosteroids and initiate hormonal replacements as clinically indicated. 	
 Monitor for signs and symptoms of hypophysitis (including hypopituitarism and adrenal insufficiency)
	Grade 3 or 4	Withhold or permanently discontinue treatment ¹		
Hyperthyroidism	Grade 2	Continue treatment	
 Treat with nonselective beta-blockers (e.g., propranolol) or thionamides as appropriate 	
 Monitor for signs and symptoms of thyroid disorders.
	Grade 3 or 4	Withhold or permanently discontinue treatment ¹		
Hypothyroidism	Grade 2-4	Continue treatment	
 Initiate thyroid replacement hormones (e.g., levothyroxine or liothyroinine) per standard of care 	
 Monitor for signs and symptoms of thyroid disorders.
Nephritis associated with increased creatinine or acute kidney injury	Grade 2	Withhold treatment	
 Administer corticosteroids (prednisolone 1-2 mg/kg or equivalent) followed by taper. 	
 Monitor changes of renal function
	Grade 3 or 4	Permanently discontinue treatment		
Neurological Toxicities	Grade 2	Withhold treatment	
 Based on severity of AE administer corticosteroids 	
 Ensure adequate evaluation to confirm aetiology and/or exclude other causes
	Grade 3 or 4	Permanently discontinue treatment		
Myocarditis	Grade 1	Withhold treatment	
 Based on severity of AE administer corticosteroids 	
 Ensure adequate evaluation to confirm aetiology and/or exclude other causes
	Grade 2-4	Permanently discontinue treatment		
Exfoliative Dermatologic Conditions	Suspected Steven-Johnson syndrome (SJS), Toxic epidermal necrolysis (TEN) or Drug rash with eosinophilia and systemic symptom (DRESS)	Withhold treatment	
 Based on severity of AE administer corticosteroids 	
 Ensure adequate evaluation to confirm aetiology and/or exclude other causes

Immune-related AEs	Severity grade CTCAE v5.0	Action taken	irAE management	Monitor and follow-up
	Confirmed SJS, TEN or DRESS	Permanently discontinue treatment		
All other immune-related AEs	Persistent Grade 2	Withhold treatment	
 Based on type and severity of AE administer corticosteroids Ensure adequate evaluation to confirm aetiology and/or exclude other causes 	
	Grade 3	Withhold or discontinue treatment based on type of event. Events that require discontinuation include and not limited to: encephalitis and other clinically important irAEs (e.g. vasculitis and sclerosing cholangitis)		
	Grade 4 or recurrent Grade 3	Permanently discontinue treatment		

1. 'Withhold or permanently discontinue treatment' is at the discretion of the investigator or treating physician.

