8.7. Supportive Care

Supportive Treatment

Patients should receive appropriate supportive care as deemed necessary by the treating investigator. The following supportive treatments are recommended:

- Tumour lysis syndrome medication (e.g. allopurinol*) daily for 7 days starting 24-48 hours prior to trial treatment (first cycle only)
* rasburicase can be used as per local policy
- Antiviral prophylaxis (e.g. aciclovir) for the duration of treatment and for 3 months after completion
- PCP prophylaxis: Local PCP prophylaxis policy should be followed
- Moderate anti-emetic risk: Local anti-emetic policy should be followed

Suggested supportive care measures for the management of adverse events with potential immunologic aetiology are outlined above (section 8.4). Where appropriate, these guidelines include the use of oral or intravenous treatment with corticosteroids as well as additional anti-inflammatory agents if symptoms do not improve with administration of corticosteroids. Note that several courses of steroid tapering may be necessary as symptoms may worsen when the steroid dose is decreased. For each disorder, attempts should be made to rule out other causes such infection, which might require additional supportive care. The use of corticosteroids as supportive care for any other indication, such as anti-emetic therapy, during study is not permitted (see section 8.8 below).

G-CSF/transfusions may be given prior to treatment (including during screening) at the discretion of the local investigator as per local practice.

Concomitant Medication

Concomitant medication may be given as medically indicated at the local investigator's discretion.

Viral Hepatitis

Serious or life-threatening reactivation of viral hepatitis may occur in subjects treated with rituximab. Therefore, subjects who are anti-HB core positive, or have a known history of HBV infection, should receive prophylaxis as per local policy.

Vaccines

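### Section 8.4.2 sets no steroid-dose condition for restarting treatment after an immune-related hold, and restart falls due at the point where a steroid taper of at least 4 weeks begins

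*Combined protocol and SAP*

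**What the plan says.** **Restart.** Section 8.4.2 directs that after a hold "treatment should resume once the adverse event has reduced to grade 1 or 0 (as per table below"). The table it points to gives event, grade, action, management and monitoring. It has no restart column and no steroid dose for restart.

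**Taper.** The following sentence reads "Corticosteroid taper should be initiated upon the adverse event improving to grade 1 or less and continue to taper over at least 4 weeks". The method of tapering is left to local practice.

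**Initial dose.** For pneumonitis and diarrhoea/colitis the table gives an "initial dose of 1-2 mg/kg prednisolone or equivalent", and the nephritis row uses the same range. Grade 2 liver events have an "initial dose of 0.5- 1 mg/kg prednisolone or equivalent". The remaining rows state no dose.

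**Both drugs.** Section 8.4.1 says "In case of a treatment delay, both drugs should be withheld", so they also restart together.

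**The steroid threshold.** Section 8.4.1 says that "if corticosteroids cannot be reduced to ≤ 10 mg prednisolone or equivalent per day within 12 weeks then treatment should be permanently discontinued". Section 8.5 repeats this among the reasons for stopping.

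**Warnings.** Section 8.7 says "Note that several courses of steroid tapering may be necessary as symptoms may worsen when the steroid dose is decreased". Section 8.8 restricts steroids on trial because they may interfere with the pharmacodynamic activity and efficacy of pembrolizumab, but exempts those given for immune-related toxicity.

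**The concern.** Restart and taper share one trigger, grade 1 or lower. Because the text says that treatment should resume at that grade, it is a direction and not only a permission. A site that follows it can give both drugs while the patient is still on a treatment dose of steroid.

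The first stake is patient safety. An event that has reached grade 1 on steroid may not yet be shown to stay there without it, and section 8.7 anticipates worsening as the dose falls. Pembrolizumab may then already have been given again. The second is the steroid restriction in section 8.8. The protocol wants steroids kept low around pembrolizumab, yet the case in which doses are highest has no ceiling at re-dosing.

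**Working it through.** The plan states no figure on this point, so the check is a comparison of the rules followed by an illustration of size.

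**1. Does any section supply a steroid limit for restart?**

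- 8.3.1, criteria before each cycle: neutrophils, platelets, AST or ALT (2.5 x ULN), bilirubin (1.5 x ULN). No steroid item.
- 9.2.1, assessments before each cycle: these include examination, adverse event check and ECG. No steroid ceiling.
- 8.4.1, general: resume on resolution; the investigator may delay for substantial clinical risk. No dose.
- 8.4.1 and 8.5, 10 mg/day within 12 weeks: a test for stopping permanently. It leaves dosing above 10 mg/day open before week 12.
- 8.8: immune-related toxicity is exempt.

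None does.

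**2. Dose when restart is first allowed (upper bound).** If the initial dose is held until the taper starts, as the order of 8.4.2 implies, the dose is mg/kg x weight. It exceeds 10 mg/day above 10/1 = 10 kg (1 mg/kg) or 10/0.5 = 20 kg (0.5 mg/kg), so in any adult. At an assumed 50-100 kg:

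- 1-2 mg/kg: 50-200 mg/day, or 5-20 times 10 mg.
- 0.5-1 mg/kg: 25-100 mg/day, or 2.5-10 times 10 mg.

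**3. Dose at the next infusion.** Cycles are 3 weeks and the taper at least 4, so a restart that follows the schedule falls inside the taper, at day 21 at the latest. On a linear 28-day taper to zero, the day-21 dose is D x (1 - 21/28) = D/4: 12.5-50 mg/day for the first group and 6.25-25 mg/day for liver events. With weekly halving it is D/8: 6.25-25 and about 3.1-12.5 mg/day. The dose at re-dosing therefore runs from the full initial dose down to values that can lie below 10 mg.

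**4. Day on which the dose is at or below 10 mg/day.** A linear taper over L days gives L x (1 - 10/D).

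| Initial dose D (mg/day) | Linear, 28 days | Weekly halving, 28 days | Linear, 56 days |
|---|---|---|---|
| 25 | 16.8 | 14 | 33.6 |
| 50 | 22.4 | 21 | 44.8 |
| 100 | 25.2 | 28 | 50.4 |
| 200 | 26.6 | 28 | 53.2 |

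Waiting for 10 mg/day thus adds about 14-28 days with the shortest taper allowed, or about 34-53 days with an assumed 56-day linear taper.

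**5. Effect on dosing before week 24 (day 168; day 0 is cycle 1 day 1).** Pembrolizumab is planned on days 1, 21, 42, 63, 84, 105, 126 and 147, which is 8 doses. Rituximab is planned on days 0, 7, 14, 21 and 105, which is 5 doses.

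Add a wait W to an existing hold of 0-63 days starting at any of cycles 2-8, and count pembrolizumab doses that no longer fall before day 168:

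- W = 14 or 17: 0-1.
- W = 22 to 34: 0-2.
- W = 53: 0-3.

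For example, after a 20-day hold starting at or before cycle 7, cycles 7 and 8 fall on days 146 and 167. A further 22 days moves them to 168 and 189, so two are lost.

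If the only delay before cycle 6 is the added 14-28 days, its rituximab dose moves from week 15 to (105 + 14)/7 = 17 or (105 + 28)/7 = 19. It stays before week 24 unless total delay reaches 168 - 105 = 63 days.

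**The case against.** The best counter-argument is that the intended level can be read from the plan. Section 8.4.1 joins resolution of the event and reduction to 10 mg/day in one 12-week limit, and a careful investigator may take the two together as what ends a hold. The pre-cycle checks and the duty to delay for clinical risk also apply. This limits the point: a reader might infer that restart depends on grade alone, and it does not. It still leaves the default rule without a steroid condition, because the 12-week test says when to stop and not when to resume.

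Section 8.8 ends by disallowing medications barred by the exclusion criteria and by requiring investigator, sponsor and participant to agree to continued treatment. Immunosuppressive therapy is among the exclusions. Whether this reaches steroids that the same section exempts is arguable, and it sets no dose.

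The 5-20 times figure is a ceiling. It needs the full initial dose at the moment of restart. By the next scheduled infusion part of the taper may have passed, and step 3 shows that the dose may then be below 10 mg. That part of the objection stands.

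A reader might also infer that early re-dosing matters because a taper flare could not be told from re-challenge toxicity, and that this decides who must stop. The documents do not support it. The pneumonitis row stops treatment for "Grade 3 or 4, or recurrent Grade 2" whatever the cause, and recurrent grade 3 diarrhoea/colitis is handled in the same way. The required action does not turn on attribution.

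Finally, the plan uses 10 mg/day at entry and at discontinuation, not at restart. Choosing it for restart is a judgment from within the protocol; no outside standard is relied on.

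**Conclusion.** The point holds as a gap in the default restart rule, with a safety consequence, and it should be closed. It is not a contradiction between sections: the restart, taper and discontinuation rules can all be followed at once.

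That no section sets a steroid limit for restart rests on the text alone. The sizes rest on assumptions: the initial dose held until the taper starts, body weight of 50-100 kg, and linear or halving tapers of 28 or 56 days. No figure is given for events with no stated steroid dose. A reader might go further and infer that many patients will be re-dosed on high-dose steroid, or that the 24-week response rate will be distorted. The documents give no basis for estimating either.

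**What to change.** In section 8.4.2, after the grade condition for restart, add: *and corticosteroids given for the event have been reduced to ≤ 10 mg/day prednisolone or equivalent (single-dose rituximab premedication and physiologic hormone replacement excepted)*. The exceptions are needed because section 8.3.5 suggests a glucocorticoid before rituximab, and the hypophysitis row of the 8.4.2 table calls for hormone replacement.

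The cost falls only on patients with such a hold. Restart of both drugs is delayed by up to about 2-4 weeks under the assumed 28-day taper, longer with slower tapers, and less if the next dose falls due after the taper has begun. This may move 0-2 of the 8 pembrolizumab doses planned before week 24 past that point (0-3 with the 56-day taper). Section 8.4.1 delays cycles and does not omit them.

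No steroid-related discontinuations are added, because patients who cannot reach 10 mg/day within 12 weeks must already stop. This takes the 12 weeks to run from the hold and not to begin again at a restart dose. The sample size of 42 and the threshold of 23 responses are unchanged.

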8.4.3. Pembrolizumab Infusion-related reactions

Pembrolizumab may cause severe or life-threatening infusion-reactions including severe hypersensitivity or anaphylaxis. Signs and symptoms usually develop during or shortly after drug infusion and generally resolve completely within 24 hours of completion of infusion. Dose modification and toxicity management guidelines on pembrolizumab associated infusion reaction are provided below:

Infusion Related Reaction Grade CTCAE v5.0	Treatment	Premedication at Subsequent Dosing
Grade 1 "Mild reaction; infusion interruption not indicated; intervention not indicated"	Increase monitoring of vital signs as medically indicated until the participant is deemed medically stable in the opinion of the investigator.	None
Grade 2 "Requires therapy or infusion interruption but responds promptly to symptomatic treatment" (e.g., antihistamines, NSAIDs, opiates, IV fluids); prophylactic medications indicated for ≤24 hrs	Stop Infusion. Additional appropriate medical therapy may include but is not limited to: IV fluids Antihistamines NSAIDs Paracetamol Opiates Increase monitoring of vital signs as medically indicated until the participant is deemed medically stable in the opinion of the investigator. If symptoms resolve within 1 hour of stopping drug infusion, the infusion may be restarted at 50% of the original infusion rate (e.g. from 100 mL/hr to 50 mL/hr). Otherwise dosing will be held until symptoms resolve and the participant should be premedicated for the next scheduled dose. Participants who develop Grade 2 toxicity despite adequate premedication should be permanently discontinued from further study drug treatment.	Participant may be premedicated 1.5h (± 30 minutes) prior to infusion of pembrolizumab with: Chlorphenamine 50 mg po (or equivalent dose of antihistamine). Paracetamol 500-1000 mg po (or equivalent dose of analgesic).
Grades 3 or 4 Grade 3: "Prolonged (i.e., not rapidly responsive to symptomatic medication and/or brief interruption of infusion); recurrence of symptoms following initial improvement; hospitalization indicated for other clinical sequelae" (e.g., renal impairment, pulmonary infiltrates) Grade 4: "Life-threatening; pressor or ventilatory support indicated"	Stop Infusion. Additional appropriate medical therapy may include but is not limited to: Adrenaline** IV fluids Antihistamines NSAIDs Paracetamol Opiates Oxygen Pressors Corticosteroids Increase monitoring of vital signs as medically indicated until the participant is deemed medically stable in the opinion of the investigator. Hospitalization may be indicated. **In cases of anaphylaxis, adrenaline should be used immediately. Participant is permanently discontinued from further study drug treatment.	No subsequent dosing
Appropriate resuscitation equipment should be available at the bedside and a physician readily available during the period of drug administration.		

8.4.4. Other pembrolizumab related adverse events

Any pembrolizumab related adverse events not included in the tables above should be managed as follows:

Adverse Event	Severity grade CTCAE v5.0	Action taken	AE management	Resume treatment
Any other pembrolizumab related AE	Grade 3 ¹	Withhold treatment	Treat AE as per local policy	When event resolves to grade 1 or 0
	Grade 4 ²	Permanently discontinue treatment	Treat AE as per local policy	

1. *Excluding fatigue, alopecia, and electrolyte disturbances that can be corrected and are unlikely to cause clinical safety concerns.*
 2. *Excluding neutropenia <7 days, lymphopenia, amylase abnormalities that are not associated with clinical symptoms, grade 4 drug-related endocrinopathy AEs which are adequately controlled with physiologic hormone replacement, and electrolyte abnormalities that can be corrected and are not felt to be a cause for clinical safety concern.*

8.4.5. Rituximab related adverse events and Infusion related reactions

Dose reductions for rituximab are not permitted.

Refer to the appropriate rituximab SPC for rituximab related adverse event and infusion related reaction dose and AE management. If rituximab treatment is withheld on a cycle where pembrolizumab is administered, pembrolizumab should also be withheld and the cycle delayed until rituximab treatment can be continued.

All patients should also be monitored for toxicity including infusion related reactions (IRR), tumour lysis syndrome (TLS), progressive multifocal leukoencephalopathy (PML); infections; Stevens-Johnson syndrome (SJS); hyperglycaemia; renal and hepatic impairment; cardiac toxicity. Special precautions for use relating to these conditions and guidance for appropriate action are provided in the SPC.

8.4.6. IgM flare

If there are any clinical or laboratory concerns about IgM flare in the first 2 cycles, plasmapheresis/other supportive care may be instituted and the subject may remain on trial treatment.

If at any timepoint after the end of cycle 2 plasmapheresis is required for symptomatic relief of IgM flare (or for any other reason), then the patient will have to cease study therapy and be managed as per standard of care at their institution.

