17. STATISTICS

17.1. Sample Size Calculation

The primary endpoint is the overall response rate (defined as complete response (CR), very good partial response (VGPR), partial response (PR) or minor response (MR) i.e. a greater than 25% reduction in the serum IgM level) by 24 weeks post commencing treatment.

It is thought the response rate could be around 60% but a rate of more than 40% is needed for this combination to be taken forward into a larger study. Using an A'Hern phase II trial design with a 1-sided alpha of 0.05 and power of 80% we will require 42 patients. The primary endpoint will be met if we see 23 or more responses.

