17.2. Statistical analysis

17.2.1. Analysis of primary endpoint

The primary endpoint is the overall response rate (defined as complete response (CR), very good partial response (VGPR), partial response (PR) or minor response (MR) i.e. a greater than 25% reduction in the serum IgM level) by week 24 post commencing treatment. This will be presented as a percentage with 90% confidence interval. We do not expect missing response data at this time point (in this patient population) to be a problem, however, if it occurs it will be treated in the following way:

Response data before 24 weeks	24 week response	Clinical status at week 24	Response
Response reported at an earlier time point	Missing	Alive with no progression reported	Responder
No response at earlier time points	Missing	Any	Non responder
Any	Missing	Progressed or died	Non responder

Any patient who does not start trial treatment will be excluded and replaced.

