APPENDIX 3: RESPONSE ASSESSMENT*

Response category	Definition
Complete response (CR)	
 • Absence of serum monoclonal IgM protein by immunofixation • Normal serum IgM level^a • Complete resolution of lymphadenopathy and splenomegaly if present at baseline • Morphologically normal bone marrow aspirate and trephine biopsy
Very Good Partial Response (VGPR)	
 • Detectable monoclonal IgM protein • $\geq 90\%$ reduction in serum IgM level from baseline^b • Complete resolution of extramedullary disease, i.e. lymphadenopathy/splenomegaly if present at baseline • No new signs or symptoms of active disease
Partial response (PR)	
 • Detectable monoclonal IgM protein • $\geq 50\%$ but $<90\%$ reduction in serum IgM level from baseline^b • Reduction in extramedullary disease, i.e. lymphadenopathy/splenomegaly if present at baseline • No new signs or symptoms of active disease
Minor response (MR)	
 • Detectable monoclonal IgM protein • $\geq 25\%$ but $<50\%$ reduction in serum IgM level from baseline^b • No new signs or symptoms of active disease
Stable disease (SD)	
 • Detectable monoclonal IgM protein • $<25\%$ reduction and $<25\%$ increase in serum IgM level from baseline^b • No progression in extramedullary disease, i.e. lymphadenopathy/splenomegaly • No new signs or symptoms of active disease
Progressive disease (PD)	
 • $\geq 25\%$ increase in serum IgM level^{a,b} from lowest nadir^c and/or • Progression in clinical features attributable to the disease

*Owen et al, 2013

^aIgM responses/progression should be confirmed by a second measurement (ideally taken within the same cycle as the initial measurement)

^bSequential changes in IgM levels may be determined either by IgM protein quantitation by densitometry or total serum IgM quantitation by nephelometry

^cThe effects of any plasmapheresis should be considered when determining the lowest nadir

Note: where local investigations are inconclusive in determining progression, or the Site are uncertain that the progression in clinical features is attributable to the disease, the TMG should be contacted for advice. In these circumstances please email [contact].

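### A patient taken off therapy for plasmapheresis after cycle 2 has no assigned response status, so a post-exchange IgM can count as a response

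*Combined protocol and SAP*

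**What the plan says.** Section 8.4.6 treats plasmapheresis differently by time. For concerns about flare in the first two cycles, "plasmapheresis/other supportive care may be instituted and the subject may remain on trial treatment". If it is needed after the end of cycle 2, for flare symptoms or any other reason, "then the patient will have to cease study therapy and be managed as per standard of care at their institution". Section 8.5, which lists reasons for permanent discontinuation, does not mention plasmapheresis.

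Appendix 3 defines minor response (MR), partial response (PR) and very good partial response (VGPR) mainly by the percentage fall in serum IgM from baseline, starting at 25%, and also requires no new clinical evidence of active disease. Its only reference to plasmapheresis is footnote c, attached to progressive disease (PD): the "effects of any plasmapheresis should be considered when determining the lowest nadir".

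Section 17.2.1 does not mention plasmapheresis. Row 1 of its missing-data table covers a patient with "Response reported at an earlier time point", no week-24 response, and alive without reported progression; that patient is a responder.

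The endpoint is worded as response *at* 24 weeks in 1.1 and 3.2.1, but *by* 24 weeks in 17.1 and 17.2.1. Section 17.1 states the decision rule: "The primary endpoint will be met if we see 23 or more responses".

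**The concern.** Section 8.3.3 itself recommends plasmapheresis as a means of bringing total IgM down. A low IgM after an exchange is therefore not evidence of drug effect. The plan recognises this in one direction only: footnote c can stop a rebound from an artificially low nadir being called progression, but nothing stops the artificial fall being called a response.

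The gap matters most for patients who need an exchange after cycle 2. The protocol takes them off study therapy, yet the analysis does not say that they are non-responders. At stake is the single go/no-go count of 23 in 42, where each wrongly counted patient moves the result towards success.

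**Working it through.** **Inputs**
- Section 17.1: null rate 40% ("a rate of more than 40% is needed for this combination to be taken forward into a larger study"), expected rate 60%, "1-sided alpha of 0.05 and power of 80% we will require 42 patients", cut-off 23.
- Section 8.2: 3-week cycles. Section 9.2.2: response at weeks 12 and 24 and at 1 year, timed from the start of treatment.
- Number of patients with on-study plasmapheresis: not given. One or two of 42 is assumed.

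**1. The plan's design reproduces.** With X ~ Bin(42, p):
- P(X ≥ 23 | p = 0.40) = 0.0375
- P(X ≥ 23 | p = 0.60) = 0.8032

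Forty-two patients with cut-off 23 is the smallest design meeting both limits.

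**2. Timing of an exchange in cycles 1–2.** Two cycles × 3 weeks = week 6. That is 12 − 6 = 6 weeks before the first scheduled response assessment and 24 − 6 = 18 weeks before the primary time point. Section 9.2.1 also requires IgM before every cycle, but those samples are not scheduled response assessments. They could count only if *by week 24* is read to admit them. Delayed cycles would also bring an exchange closer to week 12.

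**3. An exchange after cycle 2, followed through the rules**
- *Progression?* Not by the event alone. PD in Appendix 3 needs a rise of at least 25% from nadir or clinical progression.
- *Observed week-12 or week-24 IgM after the exchange?* If it is at least 25% below baseline and there are no new symptoms, it meets MR. No rule sets it aside.
- *Week 24 missing?* This is plausible. Section 9.2.2 falls under assessments during treatment, and the post-discontinuation list in 9.4 and the day-60 and 5-month columns of Appendix 1 contain no serum IgM. Row 1 then makes the patient a responder if a response was reported earlier, including one based on a post-exchange week-12 value.
- *Confirmation?* Appendix 3 footnote a asks for a second IgM measurement, ideally in the same cycle. Both samples can follow the same exchange.

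**4. Effect on the chance of declaring success at a true 40% rate.** Two models, with k affected patients:
- *A: k true non-responders are added to the count from all 42.* P(X ≥ 23 − k), X ~ Bin(42, 0.40).
- *B: k patients always count, and the other 42 − k respond at 40%.* P(Y ≥ 23 − k), Y ~ Bin(42 − k, 0.40).

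| k | Model A | Model B |
|---|---|---|
| 0 | 0.0375 | 0.0375 |
| 1 | 0.0706 | 0.0532 |
| 2 | 0.1225 | 0.0744 |

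Under either model, one patient takes the error above 0.05.

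**5. Cost of counting such patients as non-responders.** If k patients are forced to non-response and the rest respond at 60%, power is P(Y ≥ 23), Y ~ Bin(42 − k, 0.60): 0.803 for k = 0, 0.750 for k = 1 and 0.689 for k = 2.

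**The case against.** A reader might infer that any plasmapheresis on study, including in cycles 1–2, readily produces false responders. The documents do not support that. The on-treatment allowance ends at about week 6, well before the scheduled assessments. Section 8.3.3 defines flare as an IgM rise above 25%. If that rise is measured from baseline, going from 1.25 to 0.75 times baseline needs a fall of (1.25 − 0.75)/1.25 = 40%, still present at week 12 with no drug effect. The documents give no IgM kinetics to show such persistence. This part of the objection stands.

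For late exchanges, Appendix 3 already gives some protection. A patient exchanged for symptomatic flare will often fail the requirement of no new symptoms, or meet PD. That stands too, but it leaves the patient whose exchange has another reason, or whose symptoms are not judged new and whose rise does not qualify.

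A week-12 response that preceded the exchange is not an artefact, so automatic non-response could remove a genuine responder. This is fair, and it is why a sensitivity analysis is needed.

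Finally, 17.2.1 does not expect missing week-24 data to be a problem. That expectation is least secure for patients already off therapy, for whom a week-24 IgM is not clearly scheduled.

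**Conclusion.** The gap is real and worth closing, but narrow. The supported route is plasmapheresis after cycle 2 in a patient without new symptoms or PD: the plan assigns no response status, and its stated rules can make that patient a responder. Exchange in cycles 1–2 is a minor route that depends on the *by* wording or on delayed cycles.

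For one assumed affected patient, the chance of declaring success at a true 40% rate rises from 3.8% to 5.3–7.1%; for two, to 7.4–12.2%. The lower figures are from model B and the higher from model A. These figures are conditional on the assumed counts. It would be wrong to read them as the trial's actual error rate, because the documents do not say how often plasmapheresis is expected.

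**What to change.** Change the analysis wording only; the treatment rule in 8.4.6 stays as it is.

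1. **Section 17.2.1:** count a patient who has plasmapheresis after the end of cycle 2 and before the week-24 assessment as a non-responder for the primary endpoint, taking precedence over row 1 of the missing-data table. Add a sensitivity analysis that keeps any response confirmed before the exchange.
2. **Appendix 3:** extend footnote c so that IgM values affected by plasmapheresis, within an interval the sponsor sets and justifies, are not used to assign response or best response, as well as nadir. The length matters: four weeks from the end of cycle 2 reaches only week 10, so on the nominal schedule it would exclude neither the week-12 nor the week-24 value after an early exchange.
3. **Sections 17.1 and 17.2.1:** use *at week 24*, matching 1.1 and 3.2.1.

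The cost is a few sentences, plus plasmapheresis dates on the case report form if they are not already collected (the forms are not in the documents). A few patients may lose responder status. If they would otherwise have counted, power at 60% falls from 80% to about 75% for one or 69% for two. That is the conservative direction for a go/no-go decision.
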